3.1. Data sources

3.1.1. OPERA Cohort

The OPERA® (Observational Pharmaco-Epidemiology Research & Analysis) database and research network is a multi-site observational database built from the complete patient health records managed in EHR systems from more than 400 participating healthcare providers at 142 separate locations throughout the US (see coverage map below, [Figure 1](#)). Through their membership in OPERA, medical practices meet the Centers for Medicare & Medicaid Services (CMS) MIPS Incentive Program for Integration with a Specialized Registry. OPERA-participating physicians and ancillary healthcare providers have documented the care of over 900,000 patients in their EHRs, including over 143,000 PWH (~20% women), representing 14% of all PWH linked to care in the US.^[31] The OPERA database is refreshed from these EHR systems at each clinic daily, providing up-to-date data to both clinicians and researchers. In total, there are more than 12.7 million documented prospective visits in the EHR systems for PWH and over 4.3 million prescriptions written for ART medications. The average duration of follow-up (i.e., years of documenting patient visits prospectively in the EHR) is 4.7 years and there are over 20,000 PWH who have 10 years or more of follow-up.

Figure 1. US map of OPERA HIV+ population & CDC (2010) state-by-state estimates

3.1.2. Clinical Trials

Data from the phase 2 clinical trial TMB-202, as well as from the phase 3 trials TMB-301 and TMB-311 will be used.

TMB-202 trial

The TMB-202 trial (NCT00784147)^[28] was a phase 2b, randomized, double-blinded, multi-center, dose-response study of IBA+OBR in ART-experienced patients infected with HIV-1. The 48-week study was amended to 24-weeks. A total of 113 patients were enrolled between 2008 and 2010 in the US and Taiwan. Patients were randomized between IBA 800mg IV every two weeks (n=59) and IBA 2000mg IV every four weeks (n=54).

Trial Inclusion Criteria (criteria applicable to OPERA are underlined)

1. Are capable of understanding and have voluntarily signed the informed consent document
2. Have documented HIV-1 infection
3. Have no acquired immunodeficiency syndrome (AIDS)-defining events in the 3 months before Screening, other than cutaneous Kaposi's sarcoma or wasting syndrome due to HIV
4. Are able and willing to comply with all protocol requirements and procedures
5. Are 18 years of age or older
6. Have a life expectancy that is >6 months.
7. Have a viral load >1,000 copies/mL and documented decreased susceptibility to at least one NRTI, one NNRTI, and one PI, as measured by resistance testing
8. Are receiving a stable HAART for at least 8 weeks before Screening and are willing to continue that regimen until the Baseline Visit, OR (in the past 8 weeks) have failed and are off therapy and are willing to stay off therapy until the Baseline Visit
9. Have viral sensitivity/susceptibility to at least one agent as determined by the Screening resistance test (OSS criteria) and be willing and able to be treated with at least one agent to which the patient's viral isolate is sensitive/susceptible according to the screening resistance test
10. If sexually active, are willing to use an effective method of contraception during the study and for 30 days after the last administration of the study drug

Trial Exclusion Criteria (criteria applicable to OPERA are underlined)

1. Any active AIDS-defining illness per Category C conditions according to the CDC Classification System for HIV Infection^[13] (see Appendix D), with the following exceptions: cutaneous Kaposi's sarcoma and wasting syndrome due to HIV
2. Any significant diseases (other than HIV-1 infection) or clinically significant findings, including psychiatric and behavioral problems, determined from screening, medical history and/or physical examination that, in the investigator's opinion, would preclude the patient from participating in this study
3. Any acute illness within 1 week before the initial administration of study drug
4. Any active infection secondary to HIV requiring acute therapy; however, patients that require maintenance therapy (i.e., secondary prophylaxis for opportunistic infections) will be eligible for the study.
5. Any immunomodulating therapy (including interferon), systemic steroids, or systemic chemotherapy within 12 weeks before randomization
6. Any investigational therapy within 30 days before randomization, except for those HIV-agents available in expanded-access programs
7. Any prior exposure to ibalizumab (formerly TNX-355 and Hu5A8)
8. Any vaccination within 21 days before randomization
9. Any female patient who either is pregnant, intends to become pregnant, or is currently breastfeeding

TMB-301/TMB-311 trials

The TMB-301/311 trials (NCT02475629, NCT02707861)^[29, 32] were phase 3, single arm, multi-center studies of IBA+OBR in ART-experienced patients infected with MDR HIV-1. TMB-301 was a 24-week study and TMB-311 extended its follow-up to up to 96 weeks. All participants received 2000mg IBA IV (loading dose) as they maintained their current regimen, followed 14 days later by 800mg IBA IV every two weeks + OBR. A total of 40 patients were enrolled in TMB-301 (34 in the US, 4 in Taiwan, 2 in Puerto Rico), of which 27 US patients were enrolled into the extension study TMB-311 and continued to receive IBA+OBR at the dosage assigned in TMB-301. There were four deaths during the 24-week period of TMB-301, and two deaths during the TMB-311 period.

Inclusion Criteria (criteria applicable to OPERA are underlined)

1. Are capable of understanding and have voluntarily signed the informed consent document
2. Have documented HIV-1 infection
3. Have no AIDS-defining events in the 3 months before Screening, other than cutaneous Kaposi's sarcoma or wasting syndrome due to HIV
4. Are able and willing to comply with all protocol requirements and procedures
5. Are 18 years of age or older
6. Have a life expectancy that is >6 months
7. Have a viral load >1,000 copies/mL and documented resistance to at least one antiretroviral medication from each of three classes of antiretroviral medications as measured by resistance testing
8. Have a history of at least 6 months on antiretroviral treatment
9. Are receiving a stable highly active antiretroviral regimen for at least 8 weeks before screening and are willing to continue that regimen until Day 14, OR (in the past 8 weeks) have failed and are off therapy and are willing to stay off therapy until Day 14
10. Have full viral sensitivity/susceptibility to at least one antiretroviral agent, other than ibalizumab, as determined by the screening resistance tests and be willing and able to be treated with at least one agent to which the patient's viral isolate is fully sensitive/susceptible according to the screening resistance tests as a component of OBR¹
11. If sexually active, are willing to use an effective method of contraception during the study and for 30 days after the last administration of the study drug

Exclusion criteria (criteria applicable to OPERA are underlined)

1. Any active AIDS-defining illness per Category C conditions according to the CDC Classification System for HIV Infection (see Appendix A), with the following exceptions: cutaneous Kaposi's sarcoma and wasting syndrome due to HIV
2. Any significant diseases (other than HIV-1 infection) or clinically significant findings, including psychiatric and behavioral problems, determined from screening, medical history and/or physical examination that, in the investigator's opinion, would preclude the patient from participating in this study
3. Any significant acute illness within 1 week before the initial administration of study drug;
4. Any active infection secondary to HIV requiring acute therapy; however, patients that require maintenance therapy (i.e., secondary prophylaxis for opportunistic infections) will be eligible for the study
5. Any immunomodulating therapy (including interferon), systemic steroids, or systemic chemotherapy within 12 weeks before Enrollment
6. Any prior exposure to ibalizumab (formerly TNX-355 and Hu5A8)
7. Any vaccination within 7 days prior to Day 0/Enrollment
8. Any female patient who either is pregnant, intends to become pregnant, or is currently breastfeeding

¹ 5 patients with no active ARV other than IBA were enrolled.

9. Any current alcohol or illicit drug use that, in the investigator's opinion, will interfere with the patient's ability to comply with the study schedule and protocol evaluations
10. Any previous clinically significant allergy or hypersensitivity to any excipient in the ibalizumab formulation
11. Any radiation therapy during the 28 days before the first administration of investigational medication
12. Any Grade 3 or 4 laboratory abnormality according to the Division of AIDS (DAIDS) grading scale (Appendix B), except for the following asymptomatic Grade 3 events (triglyceride elevation; or total cholesterol elevation)

3.2. Study Population

3.2.1. Inclusion Criteria

Trial IBA+OBR group

1. Participant in TMB-202 or TMB-301/311²
2. Received 800 mg IBA every 2 weeks, with or without a loading dose

OPERA non-IBA OBR group

1. HIV-1 infection
2. 18 years or older
3. HTE (i.e., ever on a regimen containing either DTG BID or DRV BID)³
4. Documented resistance to ≥ 1 ARV from each of three ARV classes
5. Genotype information available for all the relevant gene regions (see [Error! Reference source not found.](#))
6. Viral load > 200 copies/mL at index regimen initiation
7. Not pregnant at index
8. No new ADE within 3 months before/on index (except cutaneous Kaposi's sarcoma or HIVAW)
9. No new cancer diagnosis within 12 weeks before/on index

² Participant on a FTR-containing OBR may be excluded if the OPERA non-IBA regimens do not include any FTR-containing regimens

³ HTE definition may be expanded if a larger sample size is needed

10. No IBA prescribed prior to/with the index regimen

11. Index regimen does not include

- Cabotegravir (CAB)⁴
- Fostemsavir (FTR)
- Investigational drugs

12. Viral sensitivity/susceptibility to at least one ARV in the index regimen

13. Baseline VL available (within 6 months before/at index)

14. Baseline CD4 available (within 6 months before/at index)

15. ≥ 1 VL measurement at any time after index

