All TMB-202 and TMB-301/311 trial participants randomized to 800 mg IBA every 2 weeks with or without a loading dose will be included in the main analyses. From the OPERA cohort, adult PWH with resistance from three ARV classes will be considered for inclusion (see section 3.2.1 for more details). OPERA PWH initiating a new non-IBA OBR between 01JAN2008 and 31DEC2020 will be included; person-time will be censored at the first of (a) initiation of a select potent ARV, (b) >45 days without ART, (c) 12 months after last clinical contact, (d) death, or (e) study end (i.e., extract date of the dataset; TBD). Viral suppression (i.e., <200 copies/mL) and undetectable viral load (i.e., <50 copies/ml) will be assessed at each of the timepoints of interest (i.e., weeks 24, 48, 60 and 96), using the closest measurement to the timepoint within a ± 6 -week window.

Statistical Analyses

Multiple imputation will be used to ensure that eligible OPERA participants can contribute to all timepoint analyses even if their routine clinical care resulted in viral loads being measured outside of the ranges defined in the protocol. To prevent the introduction of a bias towards the null, imputation will be performed in the OPERA non-IBA OBR group separately.^[18] 95% confidence intervals will be obtained through bootstrapping.

First, the data will be sampled with replacement to create 500 bootstrap samples. Within each bootstrap sample, multiple imputation will be implemented using chained equations, producing 10 imputed datasets per bootstrap sample.

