The use of external controls can provide valuable information and context to interpret the results of clinical trials when randomization to a control arm cannot be performed.^[17] However, careful consideration must be given to biases that may be introduced in such analyses. Regional bias, in which patient outcomes differ based on the geographic region due to differences in standard of care or demographic characteristics, can be reduced by selecting external controls in the same region where the trial was conducted.^[17] The Observational Pharmaco-Epidemiology Research & Analysis (OPERA) cohort is a large observational database electronic health record (EHR) from over 143,000 PWH across the US.

It is important to assess the comparative effectiveness of IBA compared to other regimens used in the routine clinical care of HTE PWH with MDR HIV. External comparisons of trial participants and PWH in routine clinical care may help assess the comparative effectiveness of IBA+OBR. Using a comparable external control and larger sample sizes may reduce bias and improve the power of such indirect comparisons. Therefore, an external comparison of IBA+OBR from the TMB-202 and TMB-301/311 trials and non-IBA OBR in routine clinical care in the OPERA cohort may confirm results from prior studies suggesting viral control benefits of IBA+OBR.

2. Study Objectives

Primary Objective

- I. To assess the virologic effectiveness of 800mg IBA every 2 weeks + OBR (TMB-202 & TMB-301/311 trials), compared to other ART regimens in routine clinical care (OPERA cohort), among HTE PWH.
 - External comparison (IBA+OBR in clinical trials vs. non-IBA OBR in OPERA)
 - Timepoint analysis
 - Multiple imputation of missing viral loads in OPERA
 - PS standardized mortality ratio-weighting

Sensitivity Objectives

- I. To assess the robustness of results from the primary objective to the viremia threshold for inclusion in the OPERA non-IBA OBR group (main: VL >1,000 copies/mL vs. sensitivity: VL >200 copies/mL).
- II. To replicate previous analyses of the European registry as closely as possible, taking into consideration the differences in design between the registry and OPERA datasets
 - External comparison (IBA+OBR in clinical trials vs. non-IBA OBR in OPERA)
 - Timepoint analysis
 - Complete case analysis
 - Propensity score matching (PS including baseline VL, CD4 cell count, number of potent ARVs scaled by the level of resistance, and the calendar period score)

3. Study Design

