3.3.2. Outcome Definition

Virologic outcomes:

- Viral suppression (<200 copies/mL)
- Undetectable VL (<50 copies/mL)

Timepoints of interest:

Weeks 24, 48, 60, 96 after index (closest measurement within a ± 6 -week window)

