4.5. Sensitivity Analyses

4.5.1. Impact of the viremia threshold in the OPERA non-IBA OBR group

In the TMB-202 and TMB-301/311 trials, the protocol restricted trial participation to individuals with a VL >1,000 copies/mL at baseline. However, in practice, individuals with a baseline VL ≤1,000 copies/mL were recruited. In routine clinical care, changes in regimen often occur before a threshold of VL >1,000 is reached. Therefore, to maximize the sample size and align with the population recruited in the trials, the main analysis will include PWH with a viral load > 200 copies/mL at the start of the index regimen in the OPERA non-IBA OBR group. However, to assess the impact of this more lenient threshold, a sensitivity analysis will be conducted in which the OPERA non-IBA OBR group will be restricted to PWH with a VL >1,000 copies/mL at index, as was intended for the trials.

Analyses described in sections 4.1-4.4 will be repeated after restricting the OPERA non-IBA OBR group to those with an index VL >1,000 copies/mL. New bootstrap samples and imputed datasets will be generated, within which SMR-weighted risk ratios will be estimated before being combined in a final estimate.

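### The main analysis sets an index viral-load floor for OPERA controls but none for the trial arm, so any trial participant at or below 200 copies/mL at first infusion would have no comparable control

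*Combined protocol and SAP*

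**What the plan says.** Trial arm. Section 3.2.1 lists two criteria: participation in TMB-202 or TMB-301/311, and "Received 800 mg IBA every 2 weeks, with or without a loading dose". A footnote allows exclusion of those on a fostemsavir-containing regimen; there is no viral-load criterion. The Study Design paragraph of the opening summary agrees: "trial participants randomized to 800 mg IBA every 2 weeks with or without a loading dose will be included in the main analyses". Section 5 counts all 99 of them.

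Control arm. Criterion 6 of the OPERA list in 3.2.1 is "Viral load > 200 copies/mL at index regimen initiation". Section 4.5.1 confirms that "the main analysis will include PWH with a viral load > 200 copies/mL at the start of the index regimen". The objectives, in the opening summary and in section 2, give the reverse assignment: "main: VL >1,000 copies/mL vs. sensitivity: VL >200 copies/mL".

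Parent trials. Section 3.1.2 gives the TMB-202 criterion as "Have a viral load >1,000 copies/mL and documented decreased susceptibility to at least one NRTI", and TMB-301 has the same viral-load threshold. Section 4.5.1 then says that "in practice, individuals with a baseline VL ≤1,000 copies/mL were recruited", with neither a count nor a lowest value.

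Outcome. Section 3.3.2 defines suppression as below 200 copies/mL and undetectability as below 50, each at the measurement nearest to weeks 24, 48, 60 and 96. Neither requires the person to have been above the threshold at index.

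**The concern.** The control floor sits at the endpoint threshold, and it binds one arm only. That creates two problems.

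The first is overlap. Standardized mortality ratio weighting reweights controls to resemble the treated group. If a trial participant entered at or below 200 there is no control in that range to up-weight, whatever propensity model is chosen. Viral load is in any case only a candidate covariate in sections 3.3.3 and 4.3, and an acceptable standardized difference on the mean can coexist with an empty region at the low end.

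The second is the endpoint. A trial participant who enters below 200 already meets the suppression definition before ibalizumab can act. If that person is still below 200 at the timepoint, the result is credited to the treated arm.

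No planned analysis would expose either problem. Sensitivity analysis 1 raises the floor to above 1,000 in the OPERA group only, which widens the difference in entry rules.

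**Working it through.** **Treated sample.** From section 5: 59 (TMB-202, 800 mg every two weeks) + 40 (TMB-301/311) = 99. This reproduces the stated figure and shows that nobody is removed for baseline viral load. The documents give no response rates and no power calculation, so the rest uses stated assumptions.

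**Entry rules against the endpoint.**
- Index value below 50: meets both endpoints at entry; no control available.
- Index value 50 to 199: meets the <200 endpoint but not the <50 endpoint; no control available.
- Index value exactly 200: meets neither endpoint; no control available.
- Index value above 200: controls are available if the >200 floor governs. If >1,000 governs, the range 201 to 1,000 has no controls either.

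**Size in the treated arm, overall result held fixed.** Let k of the 99 enter below 200 and all count as suppressed at the timepoint. Assume 50 of 99 suppressed in total. The overstatement factor is (50/99) / ((50 − k)/(99 − k)).

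| k | Without the k people | Factor |
|---|---|---|
| 1 | 49/98 = 0.500 | 1.010 |
| 3 | 47/96 = 0.490 | 1.032 |
| 5 | 45/94 = 0.479 | 1.055 |
| 10 | 40/89 = 0.449 | 1.124 |

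**Same question, true risk held fixed.** Let p be the suppression risk in the remaining 99 − k. Observed risk is ((99 − k)p + k)/99, and the factor is that divided by p. For example, k = 5 and p = 0.3 gives (94 × 0.3 + 5)/99 = 0.335, and 0.335/0.3 = 1.12.

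| p | k = 1 | k = 3 | k = 5 | k = 10 |
|---|---|---|---|---|
| 0.3 | 1.02 | 1.07 | 1.12 | 1.24 |
| 0.5 | 1.01 | 1.03 | 1.05 | 1.10 |
| 0.7 | 1.00 | 1.01 | 1.02 | 1.04 |

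**Later timepoints.** Section 3.2.2 follows TMB-202 through week 24, and section 3.1.2 puts 27 people in the TMB-311 extension. If only those 27 informed weeks 48 to 96, k = 1, 2 or 5 among them would give 1.09, 1.17 or 1.43 at p = 0.3, and 1.04, 1.07 or 1.19 at p = 0.5.

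These factors apply to the treated risk. They equal the factor on the risk ratio only if the weighted control risk does not move.

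**The case against.** The strongest reply is that nothing in the documents places any trial participant at or below 200 at first infusion. Both trials required more than 1,000, Table 1 shows a failing regimen before index, and the admission in 4.5.1 is satisfied by people at 201 to 1,000. The same section says the 200 floor was chosen partly to align with who was recruited, which suggests, without proving, that the trial data were consulted. This stands: a reader might infer that already-suppressed people are in the treated arm, and the documents do not support that. They show only that the rules permit it.

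Second, a low index value does not by itself make a responder. Under 3.3.2 the person must be below the threshold near the timepoint, so counting all k as suppressed is the worst case. The cumulative Kaplan-Meier estimate in 4.4 is less clear, because the plan does not say how someone who meets the event at time zero is handled.

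Third, a reader might infer that the bias must favour ibalizumab by the factors above. That does not follow. If viral load is in the propensity model, low-viral-load trial participants shift weight to controls just above 200. If those controls suppress more readily, weighted control risk rises and the risk ratio falls. The net size and sign cannot be derived from the documents.

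Fourth, the control rule does not strictly ensure that every control is unsuppressed at time zero. Criterion 13 accepts a baseline viral load from up to 6 months before index; if criterion 6 uses that value, it may be old.

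Last, section 4.3 defines the target as the people recruited to the trials, and dropping some of them alters it. This is a real cost. It is met by keeping the all-99 estimate, but that estimate rests on extrapolation wherever no control exists.

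**Conclusion.** The concern holds as a statement about the plan's rules. Controls have an index viral-load floor and the trial arm has none, the parent trials' floor is conceded not to have been kept, and no weighting can supply controls at or below 200. This is so whether the main control floor is >200 or >1,000.

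The size is unknown and may be zero. With 50 of 99 suppressed overall and everyone entering below 200 counted as suppressed, treated suppression is overstated by about 1.01 to 1.05 for one to five such people and 1.12 for ten. At a lower true risk, or if few people inform the later timepoints, the factor is larger. These are upper figures for the treated arm under the stated assumptions, not estimates of bias in the risk ratio.

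**What to change.** 1. Reconcile the main control threshold: the objectives (opening summary and section 2) against 3.2.1 and 4.5.1.
2. In 3.2.1, add to the trial group an index viral-load criterion with the same floor as the OPERA group in the main analysis, and define the baseline value identically in both arms, including the look-back window. State whether OPERA criterion 6 uses the criterion 13 value.
3. In 4.5.1, apply the >1,000 restriction of sensitivity analysis 1 to both arms.
4. Report how many of the 99 were at or below 200, and at or below 1,000, at first infusion.
5. Keep the all-99 analysis as a sensitivity analysis, noting any treated participants outside the control range.

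The cost is one eligibility line, one filter on data already held, and one further run of the bootstrap and imputation procedure for the all-99 result. The treated sample becomes 99 minus those excluded: with a >200 floor, 98, 96, 94 or 89 if 1, 3, 5 or 10 are at or below 200. If the reconciled main floor is >1,000, everyone at or below 1,000 is lost, a number also not given. The effect in the treated then refers to trial participants above the floor, which must be stated. If nobody falls at or below the floor, the result is unchanged and the report can say so.

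### OPERA eligibility has no counterpart to the trials' bars on active AIDS-defining illness and recent chemotherapy, and criterion 9 may cancel most of the Kaposi's sarcoma exemption in criterion 8

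*Combined protocol and SAP*

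**What the plan says.** Section 3.1.2 gives three separate rules in each trial that bear on this point:

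- Inclusion 3 concerns recent events. TMB-202 words it as "Have no acquired immunodeficiency syndrome (AIDS)-defining events in the 3 months before Screening", and TMB-301/311 has the same rule. Both exempt cutaneous Kaposi's sarcoma and HIV wasting.
- Exclusion 1 concerns current illness: "Any active AIDS-defining illness per Category C conditions according to the CDC Classification System for HIV Infection". It has the same two exemptions and no limit on onset date.
- Exclusion 5 concerns treatment. In TMB-202 it is "Any immunomodulating therapy (including interferon), systemic steroids, or systemic chemotherapy within 12 weeks before randomization". The TMB-301/311 version ends "systemic steroids, or systemic chemotherapy within 12 weeks before Enrollment".

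For the OPERA controls, section 3.2.1 has two related criteria. Criterion 8 is "No new ADE within 3 months before/on index", with the two exemptions carried over. Criterion 9 is "No new cancer diagnosis within 12 weeks before/on index", with no exemption and no mention of treatment. The document does not define a cancer diagnosis.

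Section 4.3 aims to make the external controls look as much like the treated group as possible. The propensity score candidates in sections 3.3.3 and 4.3 include CD4 count and viral load. They do not include AIDS history, active ADE, cancer or chemotherapy. AIDS history appears only in the list for the imputation model.

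**The concern.** Two of the three trial rules concern a person's state at entry: whether illness is active, and whether certain treatment was given recently. The two OPERA criteria ask only when something was first diagnosed. Someone diagnosed before the look-back window, but still ill or still on treatment, falls through.

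If such controls are less likely to reach suppression for reasons unrelated to ibalizumab (IBA), the control risk falls and the risk ratio moves in favour of IBA. In an external comparison without randomisation, eligibility and weighting are the only protections, and the weighting model has no variable aimed at this difference.

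Separately, criteria 8 and 9 may conflict over cutaneous Kaposi's sarcoma. One exempts it by name, and the other could exclude the same person as a new cancer case.

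**Working it through.** **1. The rules side by side**

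| Topic | Both trials (3.1.2) | OPERA (3.2.1) |
|---|---|---|
| Recent ADE | None in 3 months before screening; two exemptions | Criterion 8: none new in 3 months; same exemptions |
| Active Category C illness | Excluded whatever the onset; two exemptions | No counterpart |
| Chemotherapy, steroids, immunomodulators | Excluded within 12 weeks | No counterpart |
| New cancer diagnosis | No rule by diagnosis date | Criterion 9: none in 12 weeks; no exemption |

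Criterion 8 matches inclusion 3. Criterion 9 has the same 12-week window as exclusion 5, so it may be meant as a stand-in, but the document does not say so. None of the other 13 OPERA criteria covers either gap.

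**2. Two test cases**

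- A cancer diagnosed 5 months before index, with systemic chemotherapy continuing at index. Criterion 9 is met because 5 months exceeds 12 weeks. Criterion 8 is met because there is no new ADE within 3 months. Both trial protocols bar this person under exclusion 5.
- An ADE that began 4 months before index and is still active (not Kaposi's sarcoma or wasting). Criterion 8 is met. Both trial protocols bar this person under exclusion 1.

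**3. Kaposi's sarcoma windows**

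- Criterion 8 looks back 3 months: 3 × 365.25/12 = 91.3 days.
- Criterion 9 looks back 12 weeks: 12 × 7 = 84 days.

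All criteria must be met. If cutaneous Kaposi's sarcoma counts as a cancer diagnosis, criterion 9 removes new cases on days 0 to 84. The exemption then has effect only on about days 85 to 91, so 84/91.3 = 92% of its window is cancelled. If it is not coded as a cancer, there is no conflict.

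**4. Possible size**

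The only input from the plan is the control group of about 200 (section 5). The rest are assumptions: a share f of controls affected, suppression probability lower by d in that share, and a true suppression risk of 50% in both arms. Without weighting, control risk = 0.50 − f × d, and a true risk ratio of 1.00 reads 0.50/(0.50 − f × d).

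| f (people of 200) | d | Control risk | Risk ratio read |
|---|---|---|---|
| 1% (2) | 0.10 | 0.499 | 1.002 |
| 5% (10) | 0.30 | 0.485 | 1.031 |
| 10% (20) | 0.30 | 0.470 | 1.064 |

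For scale, take 99 treated, 200 controls and 50% risk in each. The standard error of the log risk ratio, unweighted, is √(1/99 + 1/200) = 0.123. An approximate 95% interval around 1.00 is exp(±1.96 × 0.123), or 0.79 to 1.27.

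**The case against.** Much of the case on the other side stands, and it limits what can be claimed.

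- **Intent.** Section 3.1.2 says that underlining marks the trial criteria applicable to OPERA. It is not visible in the text used here, so the sponsor may have left exclusions 1 and 5 out deliberately. The groups differ either way, but this cannot be called an oversight.
- **Feasibility.** Section 6.1 describes records kept for care, with incomplete ascertainment. A dated diagnosis is a workable proxy there, and active illness is harder to define.
- **Trial practice.** A reader might infer that affected controls are sicker than any trial participant could be. The documents do not support that. Section 4.5.1 says people at or below the 1,000 copies/mL limit were recruited, and a footnote in section 3.1.2 records five patients enrolled with no active drug other than IBA. The statement holds for the trial protocols, not for everyone enrolled.
- **Weighting.** A reader might infer that weighting leaves the difference untouched, or that standardized mortality ratio (SMR) weights magnify it through low CD4 counts. Neither is shown. CD4 and viral load may capture part of the severity, no baseline CD4 values are given, and weighting could enlarge or shrink the effect. AIDS history may be missing from the trial data, and whether someone ever had AIDS would not measure active illness anyway.
- **Mechanism.** Death and more than 45 days without antiretroviral therapy are censoring events in section 3.2.2. They are not counted as failures, so they do not directly lower the control estimate.
- **Direction.** If criterion 9 removes people with new Kaposi's sarcoma whom the trials' ADE rules allowed, it may make controls healthier and act against IBA.

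None of this supplies the missing counterparts to exclusions 1 and 5, or settles how criterion 9 treats Kaposi's sarcoma.

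**Conclusion.** The point holds as a gap in eligibility wording. Controls with an older ADE that is still active, or on chemotherapy for an older cancer, can enter although both trial protocols barred them. Criteria 8 and 9 need to be reconciled on cutaneous Kaposi's sarcoma, whose handling now depends on an undefined term.

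A reader might infer that such controls do enter in number, or that the comparison is shown to be biased towards IBA. The documents support neither. They give no counts, and the two parts of the problem may pull in opposite directions. Sicker controls alone would favour IBA. The shift of 0.2% to 6.4% in the risk ratio rests wholly on assumed inputs, and it is small beside the sampling uncertainty in the working. This is a minor point, worth making because the repair is cheap and serves the aim of section 4.3.

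**What to change.** 1. Reword criterion 9 to: *no systemic chemotherapy recorded within 12 weeks before index, and no new cancer diagnosis other than cutaneous Kaposi's sarcoma in that period*. Keep the diagnosis rule as a backstop, because chemotherapy given elsewhere may not be recorded. Define which diagnosis codes count as cancer.
2. Where OPERA records allow, add to criterion 8 the exclusion of an ADE recorded as still active or under acute treatment at index, with the existing two exemptions. State how this is identified. If it cannot be done reliably, list it as a limitation in section 6.1.
3. Count the controls who would be lost to a 12-week exclusion for systemic steroids and immunomodulators. If it costs many, apply it only as a sensitivity check.

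The cost is two reworded criteria, the matching selection code and probably a few controls from a group that section 5 already treats as possibly too small. Treatment at outside practices will still be captured incompletely, as section 6.1 implies.
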